AZD5069: Arms A2, A3, A5, A7, B2, B4, and B6: Patients will receive AZD5069 as 40 mg BID starting with Day -7 of a 7-day lead-in period at the defined dose in each treatment arm as described in the study design. Following the lead-in period, patients will receive BID dosing of AZD5069 daily for a 28-day cycle. On days when both AZD5069 and MEDI4736 are given, the morning dose of AZD5069 is administered at least 30 minutes before starting infusion of MEDI4736. For Arm A5 specifically, the sequence of dosing for the first 4 cycles was planned to be AZD5069 followed 30 minutes later by tremelimumab infused over 1 hour (± 10 minutes) followed by MEDI4736 infused over 1 hour (± 10 minutes). As discussed in the study design Arm A5, Arm A7, and the food effect substudy will not open for enrolment. In all cases, AZD5069 should be administered either 2 hours before or 2 hours after (with ± 2 hours) food consumption at approximately the same time each day.

MEDI4736: Arms A1-A7, B1-B4, B7, and B8: Patients will receive MEDI4736 starting on Day 1 of Cycle 1 and will be administered as 20 mg/kg infusion administered over 1 hour Q4W in a 28-day cycle. In addition to the above arms, patients in monotherapy Arms (B5 and B6) who develop confirmed disease progression may have MEDI4736 added, at the discretion of the Investigator and after notifying the Medical Monitor. MEDI4736 will be added to the dosing schedule beginning on Day 1 of the following treatment cycle. Thereafter, all study treatment will follow the same schedule as for a patient on a combination therapy arm. For Arm B8, a flat dose of 1.5 g will be administered. In Arms B5 and B6, MEDI4736 could be added to treatment after progression on AZD9150 or AZD5069 monotherapy agents, respectively.

Tremelimumab: Arms A4 and A5: Patients will receive tremelimumab starting Day 1 of Cycle 1 and will be administered as 1 mg/kg infusion administered over 1 hour Q4W in a 28-day cycle. Tremelimumab will be infused for a maximum of 4 cycles.

Statistical methods

The dose-escalation Part A used a continual reassessment method-based approach to identify the set of AZD9150/MEDI4736 and AZD5069/MEDI4736 dose combinations where the incidence of DLT is no larger than 33%. Once the MTDs for each of the 2 agents in combination with MEDI4736 were identified or the maximum doses of each of the 2 agents in combination with MEDI4736 were reached, the SRC decided (based on emerging and maturing data) to enroll an additional 6-12 patients to Arm A3 to test alternative dosing schedule of AZD5069. Also, Arms A4, A5, A6 and A7 are designed with a small number of

patients (6 to 18) to gather and confirm safety information and will start/continue to enroll for A5 and A7, based on emerging safety and efficacy data from Part B. The dose-expansion Part B for Arms B1-B6 will use an adaptive approach to sample size based on Bayesian statistical methodology, so the number of actively enrolling treatment arms may decrease as the study continues. The maximum number of evaluable patients to be included in naïve combination arms is N=35. The maximum number of patients to be included in pretreated combination arms is N=52.

For the 2 combination arms in the anti-PD-(L)1 naïve patients (Arms B3 and B4), once 12 efficacy outcomes have been observed in the first 12 efficacy evaluable patients in each arm, a predictive power calculation will be used to assess the chance of observing at least 8 of 35 responses (either PR or CR) in each arm. The method of calculating predictive power is based on a parameter free approach to predictive power as it applies to variables that follow a binomial distribution (Jennison and Turnbull 2000). Predictive power (chance to observe at least 8 of 35 responses) will be recalculated following the observation of the efficacy outcome in each efficacy evaluable patient as they were dosed in the trial. If, following the observation of any patient's outcome, predictive power falls below 20%, the arm in which this happens will be stopped. If predictive power remains above 20% following the 19th efficacy evaluable patient, then an interim analysis will be conducted following the 20th efficacy evaluable patient. Each of the combination arms will continue to enroll patients up to a maximum of 35 efficacy evaluable patients following the interim analysis if at least 5 of 20 patients have responded with at least a PR.

Predictive power monitoring will not be performed for the 2 monotherapy groups (B5 and B6) in dose-expansion Part B and the 1L RM SCCHN patients in Arm B7. The 2 monotherapy arms will continue recruiting until 12 efficacy evaluable patients have been enrolled in each arm.

For the 2 combination arms in the anti-PD-(L)1 pretreated patients (B1 and B2), once efficacy outcomes have been observed in the first 10 efficacy evaluable patients in each arm, a predictive power calculation will be used to assess the chance of observing at least 3 of 20 responses (either PR or CR) in each arm. Predictive power (chance to observe at least 3 of 20 responses) will be recalculated following the observation of the efficacy outcome in each efficacy evaluable patient as they were dosed in the trial. If, following the observation of any patient's outcome, predictive power falls below 20%, the arm in which this happens will be stopped. However, no formal interim analysis will be conducted for the combination arms in the anti-PD-(L)1 pretreated patients.

In addition, Arms B7 and B8 will enroll patients who have not received prior systemic treatment for RM SCCHN and will receive combination treatment of AZD9150 in combination with MEDI4736. With approximately 48 patients in each arm, the chance that

fewer than 12 patients with CR or PR (responding) will be observed, given the true fraction of patients responding is 35%, is 9%. The chance that at least 15 patients responding is observed, given the true fraction of patients responding is 25%, is 20%. In addition, B8 will incorporate predictive power monitoring for futility beginning with the 15th patient. If at any time from the 15th patient through the 48th patient, the chance to observe 13 responses in 48 patients falls below 20%, then the arm will be stopped.

Recruitment will continue while predictive power is measured. If an arm is to be stopped, no new patients will be recruited to that arm, but patients who are already on study in that arm will continue in accordance with study guidelines outlined in Section 4.

TABLE OF CONTENTS

TITLE PAGE.....	1
VERSION HISTORY	2
CLINICAL STUDY PROTOCOL SYNOPSIS	9
TABLE OF CONTENTS.....	25
LIST OF ABBREVIATIONS AND DEFINITION OF TERMS.....	32
1 INTRODUCTION.....	38
1.1 Background and rationale for conducting this study	38
1.1.1 AZD9150.....	38
1.1.2 AZD5069.....	38
1.1.3 MEDI4736.....	39
1.1.4 Tremelimumab	39
1.1.5 Disease background	39

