Patients participating in the lead-in part of the study will be administered study drug 7 days before the date of the genetic sample collection. This may continue for as long as they are continuing to show clinical benefit, as judged by the Investigator, unless a patient has confirmed progression of disease (PD) with either clinical deterioration and/or no further benefit from treatment, experiences unacceptable toxicity, or discontinues for any other reason. If a patient on either monotherapy arm (treatment arms B5 or B6) has confirmed PD, they may, at Investigator's discretion and with notification to the Medical Monitor, add MEDI4736 to their treatment regimen. These patients, post addition of MEDI4736 to the monotherapy treatment will continue to be part of the safety analysis but will be censored from the efficacy analysis. After discontinuation of treatment, all patients will continue to be followed for safety, subsequent anticancer therapy, and survival. During this time, all patients will be followed for safety (including concomitant medication) for 28 days (+7 days) after the last dose of study drug or until the initiation of a subsequent anticancer therapy. In addition, patients who received MEDI4736 as part of their combination treatment will be followed for immunogenicity for 90 days (± 7 days) after the last dose of MEDI4736 or until the initiation of alternative anticancer therapy. Patients who discontinued treatment for reasons other than PD will continue to undergo tumor assessments every 2 months (± 7 days) until PD is noted. All patients will be followed for subsequent anticancer therapy every 2 months (± 7 days) and will also be followed for overall survival every 2 months (± 7 days) from the date of randomisation to the date of death due to any cause, assessed for approximately 40 months. The patients will be censored on the date of last follow-up visit.

Investigational product, dosage and mode of administration

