4.2.3 End-of-treatment evaluations and follow-up

EOT evaluations, including safety and tumor assessments, shall be performed as soon as possible following the decision to discontinue treatment (see the study event overview, [Table 5](#)).

In addition, patients should be followed up for at least 28 days (+7 days) after the last dose of study treatment for any new reports of AEs, SAEs, and concomitant medications.

Safety follow-up for IM will continue for all patients treated with MEDI4736 for 90 days (± 7 days) after the last dose of MEDI4736 or until the initiation of subsequent anticancer therapy.

Patients who discontinued treatment for reasons other than PD will continue to undergo tumor assessments every 2 months (± 7 days) until PD is noted. All patients will be followed for subsequent anticancer therapy every 2 months (± 7 days) and will also be followed for OS every 2 months (± 7 days) from the date of randomisation to the date of death due to any cause, assessed for approximately 40 months. The patients will be censored on the date of last follow-up visit.

The status of “ongoing,” “withdrawn from the study,” and “lost to follow-up” for patients at the time of an OS analysis should be obtained by the site personnel through checking the patient notes, hospital records, contacting the patient’s general practitioner, and checking publicly available death registries. If the patient has actively withdrawn consent to the processing of their personal data, the vital status of the patient can be obtained by site personnel from publicly available resources where it is possible to do so under applicable local laws.

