Progression-free survival is defined as the time from start of treatment (Cycle 1, Day 1) until the date of objective disease progression or death (by any cause in the absence of progression) regardless of whether the patient withdraws from therapy or receives another anticancer therapy before progression. Patients who have not progressed or died at the time of analysis will be censored at the time of the latest date of assessment from their last evaluable RECIST version 1.1 assessment. However, if the patient progresses or dies after 2 or more missed visits, the patient will be censored at the time of the latest evaluable RECIST version 1.1 assessment. If the patient has no evaluable visits or does not have baseline data, he/she will be censored at 0 days unless he or she dies within 2 visits of baseline.

The PFS time will always be derived based on scan/assessment dates not visit dates.

RECIST version 1.1 assessments/scans contributing towards a particular visit may be performed on different dates. The following rules will be applied:

- Date of progression will be determined based on the earliest of the dates of the component that triggered the progression
- When censoring a patient for PFS the patient will be censored at the latest of the dates contributing to a particular overall visit assessment

Overall survival

Overall survival is defined as the time from the date of Cycle 1, Day 1 until death due to any cause. Any patient not known to have died at the time of analysis will be censored based on the last recorded date on which the patient was known to be alive.

Survival at 12 months

Patients who are alive 1 year following the beginning of treatment are said to have survived 12 months. Patients whose vital status is unknown at 12 months will be censored at the last date that the patient was known to be alive.

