### 8.3.8. Overall Survival (OS)

Overall survival (OS) is defined as the time from the date of the treatment allocation (Part A) or randomization to study drug (Part B) to the date of death from any cause. OS will be estimated using K-M methodology and the Efficacy Set. Any subject not known to have died at the time of analysis will be censored based on the last recorded date that the subject was known to be alive. This date is the latest of the last known tumour assessment, the last date of collection of clinical laboratory or vital sign data, or the last date of telephone contact with the subject.

In dose-expansion Part B, some patients may be allowed to move from a monotherapy arm to a combination arm during the trial. The survival times for these patients will be censored at the date immediately prior to the date of the first dose of the combination drug.

The distribution of OS in the Efficacy Set will be displayed graphically by treatment group. The number of events and estimates for the 25%, 50% (median), and 75% percentiles for OS will be summarized by treatment group. For Part B only, two-sided 80% CIs will be provided of the median OS estimates (Brookmeyer and Crowley, 1982).

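### Three conflicting OS censoring dates; two of them keep deaths found by the vital-status check but drop proof-of-life dates, which would bias Kaplan-Meier OS downwards

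*Protocol*

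**What the plan says.** **Protocol follow-up text** (Synopsis under Duration of treatment, and Sections 3.9, 4.1.2, 4.2.2, 4.2.3 and 6.11). After describing survival follow-up every 2 months, each says "The patients will be censored on the date of last follow-up visit".

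**Protocol 8.9.** A patient not known to have died is "censored based on the last recorded date on which the patient was known to be alive". No source is excluded.

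**SAP 8.3.8.** The rule opens in the same way, with subjects "censored based on the last recorded date that the subject was known to be alive", and then defines that date: "This date is the latest of the last known tumour assessment, the last date of collection of clinical laboratory or vital sign data". The only further source it admits is a telephone call to the subject. The event runs "to the date of death from any cause. OS will be estimated using K-M methodology and the Efficacy Set", with no limit on how a death is learned of.

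**Protocol 4.2.3.** At the OS analysis, site staff establish the status of ongoing, withdrawn and lost patients from patient notes, hospital records and the general practitioner, "and checking publicly available death registries".

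SAP Section 13, which lists changes from the protocol, does not mention the OS censoring date.

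**The concern.** The three dates can differ for the same patient, and nothing in the documents says which one governs. The SAP list is the version a programmer would implement. It contains none of the sources named in Protocol 4.2.3.

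Consider two patients who stopped visits at month 5. Hospital records show that one died at month 11 and that the other was alive at month 14. Under the visit rule or the SAP list, the first is an event at month 11 and the second is censored at month 5. Follow-up found by the same check is kept for the death and discarded for the survivor, so censoring depends on the outcome. SAP 8.3.8 reports OS medians, quartiles and 80% intervals for each Part B arm, and a downward bias passes straight into them. Arms with shorter follow-up would be affected more, so arms could look different for reasons unrelated to treatment.

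**Working it through.** The plan states no OS target, event count or power, so there is no OS figure to reproduce. The check has two parts: direction, then size.

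**Direction.** Kaplan-Meier survival is S(t) = ∏(1 − d_j/n_j), with d_j deaths and n_j patients at risk at each death time. Under the visit rule or the SAP list, the d_j include deaths found by the check. The n_j lose patients whom the check shows to be alive beyond their last listed date. Each affected factor is therefore too small, and S(t) is too low. Under Protocol 8.9 those patients stay in n_j and the bias does not arise.

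**Size, by simulation.** Inputs from the documents:
- Survival contact every 2 months (Synopsis).
- Cut-off 6 months + 90 days after the last patient starts, about 9 months (Protocol 6.12).
- Median OS of 7.4 and 10.1 months, from the published first-line trial cited in Protocol 1.1.5.

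Assumptions:
- Exponential survival, with an added 14-month median.
- Uniform accrual over 12 or 24 months, giving cut-offs 9–21 or 9–33 months after entry.
- A check that finds every patient's status.
- 0%, 10% or 20% of patients stopping visits at a random time.

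Each scenario used 400,000 patients. The reference column censors survivors at the check. The other columns count the same deaths but censor survivors at the last 2-monthly visit. Entries are 12-month OS (%).

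| Median (months) | Cut-off (months) | Reference | 0% stop | 10% stop | 20% stop | Drop at 20% (points) |
|---|---|---|---|---|---|---|
| 7.4 | 9–21 | 32.5 | 31.5 | 30.5 | 29.5 | 3.0 |
| 10.1 | 9–21 | 43.9 | 42.9 | 41.8 | 40.6 | 3.3 |
| 14 | 9–21 | 55.2 | 54.3 | 53.1 | 51.9 | 3.3 |
| 7.4 | 9–33 | 32.5 | 32.0 | 31.5 | 31.0 | 1.5 |
| 10.1 | 9–33 | 44.0 | 43.5 | 42.8 | 42.1 | 1.9 |
| 14 | 9–33 | 55.2 | 54.8 | 54.1 | 53.3 | 1.9 |

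For a 10.1-month median and the 9–21 window, the estimated median falls from 10.08 to 9.48 months at 20% stopping.

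**Shorter follow-up.** Arm B8 entered the protocol in mid-2018. Counting from Amendment 9 (24 August 2018) to the 28 February 2020 cut-off gives about 18 months at most. With cut-offs of 9–18 months, 20% stopping (last contact uniform from month 1) and medians of 7, 10 and 12 months, 12-month OS goes from 30.4 to 27.1, 43.6 to 40.0 and 50.0 to 46.4. These are drops of 3.3, 3.6 and 3.6 points.

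**Where it is small.** With nobody stopping visits, the 9–18 window and contact only every 2 months, the drop is about 1.4 points. With fortnightly contact, close to the Day 1 and Day 15 laboratory tests in Protocol 5.4.1, it is about 0.3. With cut-offs of 18–40 months it is 0 to 1 point, even at 40% stopping.

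**Is the asymmetry the cause?** If deaths after the last visit are ignored as well, so that both sides lose the check, the simulated curve returns to the reference. For a 10.1-month median, 9–21 window and 20% stopping, it gives 44.0% against 43.9%.

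**The case against.** - **The analysis section does not use the visit rule.** Protocol 8.9 and the opening words of SAP 8.3.8 both say last known alive. The repeated follow-up sentence could be read loosely as the last survival contact. This stands, and it makes the bias conditional. A reader might infer that OS in this trial is biased low. The documents do not support that, because one of the three rules is free of the problem. They do not say that this rule prevails.
- **The asymmetry is partly inferred.** No text says that deaths found by the check count and alive findings do not. It follows from an event definition without a source limit and a closed list of alive dates. Protocol 4.2.3 asks for a status and does not mention a last-alive date.
- **Death registries.** A reader might include patients whom a registry search shows to be alive. A death registry records deaths, and absence from it is not dated proof of life. The affected patients are those confirmed alive by notes, hospital records or the general practitioner.
- **The gap is narrow.** Telephone contact with the subject is on the SAP list, and patients on treatment have frequent laboratory dates. The loss falls mainly on withdrawn or lost patients.
- **Consequence.** OS is secondary and descriptive, with no between-arm test (SAP Section 8) and no decision rule. An exact 80% interval for 24 of 48 patients is about 40% to 60%, so a shift of 1 to 3 points is small beside sampling error. It is, however, systematic and avoidable.
- **The 12-month proportion.** SAP 8.3.9 counts unknown status as dead, which is a separate rule. The figures here concern the Kaplan-Meier 12-month estimate planned in Protocol 8.10.

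**Conclusion.** The conflict between the three rules is certain from the text. The downward bias follows if the visit rule or the SAP list is applied and deaths found by the vital-status check are counted. It does not follow under Protocol 8.9.

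With 20% of patients stopping visits, 12-month OS would be about 1.5 to 3.6 points too low. The upper end belongs to cut-offs 9–18 months after entry, as may apply to B8, and the lower end to cut-offs spread over 9–33 months. It is about 1 point or less when few are lost and contact is frequent, or when follow-up is long. The loss fraction, exponential survival, accrual pattern and complete vital-status check are all assumptions. The point deserves correction because it changes a reported estimate and is cheap to settle. It does not touch the primary endpoint.

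**What to change.** Use the Protocol 8.9 rule throughout.

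1. In SAP 8.3.8, replace the closed list with: *the latest date, on or before data cut-off, on which the patient is documented to be alive from any source, including study visits and assessments, survival follow-up contacts, patient or hospital notes, and general practitioner contact.*
2. Count deaths only up to the same data cut-off.
3. In Protocol 4.2.3, have sites record the date last known alive as well as the status. State that absence from a death registry is not proof of life.
4. Delete or align the last-follow-up-visit sentences in the Synopsis and Sections 3.9, 4.1.2, 4.2.2, 4.2.3 and 6.11.

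The cost is a few sentences of text and one more date for sites to record during a check they already have to make.

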AUC _(0-∞)	Area under the plasma concentration-time curve from zero to infinity
β-hCG	Beta human chorionic gonadotropin
BCRP	Breast cancer resistance protein
BID	Bis in die (i.e., twice daily)
BP	Blood pressure
CD	Cluster of differentiation
cEt	Constrained ethyl
cfDNA	Circulating-free deoxyribonucleic acid
CI	Confidence interval
CL	Clearance
CL/F	Apparent plasma clearance

Abbreviation or special term	Explanation
CL _p	Plasma clearance
CL _{ss} /F	Apparent plasma clearance at steady state
C _{max}	Maximum plasma concentration
CR	Complete response
CRF	Case report form (electronic/paper)
CRM	Continual reassessment method
CSP	Clinical Study Protocol
CSR	Clinical Study Report
C _{ss max}	Maximum plasma concentration at steady state
C _{ss min}	Minimum plasma concentration at steady state
CT	Computerised tomography
CTCAE	Common Terminology Criteria for Adverse Events
CTLA4	Cytotoxic T-lymphocyte-associated protein 4
C _{trough}	Concentration at the end of a dosing interval
CXCR2	CXC chemokine receptor-2
CYP	Cytochrome P450
D	Day
DCR	Disease control rate
DILI	Drug-induced liver injury
DLBCL	Diffuse large B-cell lymphoma
DLT(s)	Dose-limiting toxicity(ies)
DNA	Deoxyribonucleic acid
DOR	Duration of response
ECG	Electrocardiogram
ECL	Electrochemiluminescence
ECOG	Eastern Cooperative Oncology Group
eCRF	Electronic case report form
EOT	End-of-Treatment
FDA	Food and Drug Administration
GCP	Good Clinical Practice
GGT	Gamma-glutamyl transpeptidase

Abbreviation or special term	Explanation
gmean	Geometric mean
GRO- α	Growth regulated oncogene-alpha
h	Hour(s)
HBV	Hepatitis B virus
HCV	Hepatitis C virus
HCC	Hepatocellular carcinoma
HIV	Human immunodeficiency virus
HPF	High-power field
HL	Hy's Law
IATA	International Air Transport Association
IB	Investigator's Brochure
IBW	Ideal body weight
ICF	Informed Consent Form
ICH	International Conference on Harmonisation of Technical Requirements for Registration of Pharmaceuticals for Human Use
IEC(s)	Independent Ethics Committee(s)
Ig	Immunoglobulin
IgG1 κ	Immunoglobulin G1 kappa
ILD	interstitial lung disease
IM	Immunogenicity
imAE	Immune-mediated adverse events
IP	Investigational product
irAE	Immune-related adverse events
IRB(s)	Institutional Review Board(s)
IV	Intravenous(ly)
IWRS	Interactive web-based randomisation system
kg	Kilogram(s)
KM	Kaplan-Meier
L	Litre(s)
LDH	Lactate dehydrogenase
mAb(s)	Monoclonal antibody(ies)
MDSC(s)	Myeloid-derived suppressor cell(s)

Abbreviation or special term	Explanation
MedDRA	Medical Dictionary for Regulatory Activities
mg	Milligram
min	Minute(s)
mL	Millilitre
MRI	Magnetic resonance imaging
mRNA	Messenger ribonucleic acid
MRT _{last}	Mean residence time
MTD(s)	Maximum tolerated dose(s)
NC	Not calculated
NCI	National Cancer Institute
NE	Not evaluable
NTL	Nontarget lesion
OAE(s)	Other significant adverse event(s)
ORR	Objective response rate
OS	Overall survival
P-gp	P-glycoprotein 1 (also known as multidrug resistance protein 1)
PD	Progression of disease
PD-1	Programmed cell death 1 (CD279)
PD-L1	Programmed cell death-ligand 1 (also known as B7 homolog 1, CD274)
PD-(L)1	Programmed cell death 1 (CD279) and/or programmed cell death-ligand 1 (also known as B7 homolog 1, CD274)
PDRNA	Pharmacodynamic RNA
PFS	Progression-free survival
PHL	Potential Hy's Law
PK	Pharmacokinetic(s)
PO	Per os (i.e., by mouth)
PR	Partial response
PS	Performance status
Q2W	Every 2 weeks
Q3W	Every 3 weeks
Q4W	Every 4 weeks

Abbreviation or special term	Explanation
QT	ECG interval measured from the onset of the QRS complex to the end of the T wave
QTc	Corrected QT interval
QTcF	Calculated QTc using Fridericia's formula
QW	Every week
R _{ac}	Extent of accumulation on multiple dosing
RBC	Red blood cell(s)
RECIST	Response Evaluation Criteria in Solid Tumors
RM	Recurrent and/or metastatic
RNA	Ribonucleic acid
RP2D	Recommended Phase 2 dose
SAE(s)	Serious adverse event(s) (see definition in Section 6.2)
SC	Subcutaneous
SCCHN	Squamous cell carcinoma of the head and neck
SD	Stable disease
SGOT	Serum glutamic oxaloacetic transaminase
SGPT	Serum glutamic-pyruvic transaminase
sPD-L1	Soluble programmed cell death-ligand 1
SRC	Safety Review Committee
STAT3	Signal Transducer and Activator of Transcription 3
SUSAR	Suspected unexpected serious adverse reaction
t _{1/2}	Concentration half-life
t _{1/2λz}	Terminal (elimination) half-life
T3	Triiodothyronine
T4	Thyroxine
TBD	To be determined
TBL	Total bilirubin
TEAE(s)	Treatment-emergent adverse event(s)
TGI	Tumor growth inhibition
TL	Tumor lesion
T _{max}	Time to reach C _{max}
TMG	Toxicity Management Guidelines

Abbreviation or special term	Explanation
TSH	Thyroid-stimulating hormone
$T_{ss \max}$	Time to reach C_{\max} at steady state
Tx	Treatment
ULN	Upper limit of normal
V_1	Central volume of distribution
V_d/F	Apparent volume of distribution
V_{ss}	Apparent volume of distribution after intravenous distribution
V_{ss}/F	Apparent volume of distribution after oral administration
V_z/F	Apparent volume of distribution
WBC	White blood cell(s)
WBDC	Web-based data capture

